5.0 Adherence

Few studies have examined the relationship between medication adherence and sustained virological response (SVR) in treatment of chronic hepatitis C. In post-hoc analyses, McHutchison et al. ¹⁷ showed nonstatistical differences in SVR according to adherence as defined by pharmacy records and pill counts. Among individuals who received 80% or more of their total interferon dose, with 80% or more of the ribavirin dose, for 80% or more of the expected duration of therapy (80-80-80), 48% achieved SVR as compared to 41% from the intent-to-treat analysis of the original study. Similar increases in SVR were observed in subgroups defined according to genotype. In addition, the dose of ribavirin administered appears to be critical in achieving SVR. Only 28% of individuals who received ribavirin at a dose of less than 10.6 mg/kg/day (800 mg/day) achieved SVR as compared to 44% when greater than 10.6 mg/kg/day was taken. Taken together, these findings suggest that poor adherence, particularly to ribavirin, will lead to lower rates of SVR. McHutchison et al. ⁶ also showed the effect of adherence on SVR with pegylated interferon and ribavirin. In another post-hoc analysis, the investigators showed that 63% of participants with 80-80-80 adherence, taking a dose of 10.6 mg/kg of ribavirin or more, achieved SVR as compared with 54% from the intent-to-treat analysis of the original study.

Nevertheless, it remains unclear if adherence is a factor that explains the low SVR observed in African Americans as compared to Caucasians. In the studies by McHutchison et al., ^{6,17} adherence differences between African Americans and whites were not reported. However, the number of African Americans enrolled in these and other studies was very small and therefore it is difficult to draw definitive conclusions about adherence in African Americans and effects on SVR. Moreover, previous studies in HCV have used relatively crude measures of medication adherence or not measured adherence at all (e.g., Younossi et al.) ¹⁸; as a result, it is unclear whether measurement bias may be a factor in explaining the apparent effects of poor adherence. Therefore, the relationship of adherence and SRV needs to be studied in greater detail using a prospective study design.

5.1 Adherence Measures

Electronic Monitoring

Microprocessor technology is now being used in a high-technology approach to electronically monitor and measure adherence. When used correctly, electronic monitoring is considered the consummate technology for assessing adherence.¹⁹⁻²¹ The most common type of electronic monitor is known as the Medication Event Management System (MEMS). MEMS uses a computer chip in the cap of a medication vial that records the precise date and time the vial was opened and presumably when the drug was taken. Electronic monitoring provides information about drug intake behavior that cannot be obtained from medical histories or from clinical laboratory examination. In addition, when used correctly, electronic monitoring supplies a more reliable measure of adherence than any other measure because it provides a time series of the adherence pattern over the total treatment time. As a measure of drug exposure, electronic monitoring has been shown to be valid, sensitive, specific, and representative of adherence behavior.²²

5.2 Procedures

Patient Education and Adherence Program

The adherence program for the study will consist of three central components: (a) informational-exchange, (b) skills development, and (c) social support enlistment. One of the principle tools utilized in this study will be the Medication Adherence Training Interview (i.e., MATI), a structured interview for medication education and adherence training. The MATI has been empirically tested in behavioral medical research in an HIV population at one of the Virahep-C clinical sites and now has been modified for use in patients with chronic hepatitis C. *A copy of the MATI appears in Appendix 5.*

5.3 Baseline (Day 0). Regarding adherence, the main purpose of the baseline visit is for skills training. Participants will be encouraged to bring along a supportive partner or friend to the baseline visit. During this visit, participants will be taught: a) techniques for self-injection of peginterferon; b) self-management of side

effects; and c) basic problem solving skills. Participants will be shown a video that will explain the medication regimen including instructions on drug dosing and self-injection, scheduling of dosing, management of side effects, storage recommendations, and tips on remembering doses. After viewing the video, a clinician will briefly review the contents of the video with the participant, demonstrate proper self-injection technique, and then allow the participant to practice the technique on pads that simulate human skin and fat tissue.

During this visit the study coordinator will also engage the participant in goal setting. Participants will be asked by the coordinator to set short-term goals (e.g., achieving a near-perfect adherence rate for the next 30 days) that may be important to the efficacy and safety of antiviral therapy. Participants will also be asked to create self-incentives for attaining the stated goals. The rationale is that individuals achieve greater self-directed change if they reward their successful efforts than if they provide no incentives for themselves.

Participants will be asked to self-monitor their own adherence behaviors. Participants will be given a diary and asked to keep track of non-adherence and the events that foster it. The clinician will assist the participant with planning a dosing schedule and integrating the medication times into lifestyle patterns. Written information and a dosing card summarizing the information from the session will be provided

5.4 Study Visits. At subsequent study visits, participants will be asked about tolerance to medications and adherence will be stressed. A brief version of the MATI protocol will be followed during weeks 4, 12, 20, 28, and 36 to review how medications are taken and encourage adherence. The content of the adherence interview will include discussion of non-adherence events shown in the diary, assistance with side effect management, and support for remaining in the trial.

Structured Phone Calls/Periodic Telephone Contact

In addition to the clinic-based patient education, participants will receive a telephone call by a trained study coordinator between weeks 24 to 26. The intent is to identify problems or concerns participants may have between visits that can be addressed with study coordinators. During the call the coordinator will inquire whether the participant is having any difficulty taking medicines regularly and as prescribed. If the participant is not having difficulties, the coordinator will commend the participant's efforts, inquire if the participant has any questions, and conclude the call. If the participant is having difficulties, the study coordinator will inquire about the nature of the difficulties and record participant responses and any recommendations made.

Periodic Acknowledgements and Expressions of Gratitude

Patients will be periodically thanked for their participation through a card or letter mailed from each site. This is a low cost method that may encourage continued participation and adherence. A card or letter will be sent at weeks 12 and 36.

Adherence Data Collection

In the study, the MEMS cap will record extensive information about medication-taking behavior among participants in the clinical trial. This information will be supplemented with self-reported information collected during clinic visits. This will require, however, that the participants always take the ribavirin capsules and peginterferon syringes directly from bottles fitted with the electronic monitoring caps (explained below).

Data Collection Procedures

At the beginning of the study, the study coordinator at each of the participating sites will be shipped a supply of the electronic compliance monitoring caps. Study coordinators will be trained to provide standardized instruction on electronic monitoring system use and participants will be given printed materials that explain the system.

At day 0, the pharmacy will dispense 180 ribavirin capsules in the original bottles supplied by the pharmaceutical manufacturer. In addition, the pharmacy will also dispense five pre-filled peginterferon syringes placed inside of opaque prescription bottles that accommodate MEMS caps. Lastly, pharmacies will provide needles for injection that fit the prefilled peginterferon syringes. Lids from both the ribavirin and peginterferon bottles will be replaced by the study coordinator with child-resistant MEMS caps. The opening and closing of the MEMS caps by the participant will electronically record dosing dates and times. Monitoring caps will be color coded to avoid inadvertently switching the two caps.

Electronic monitoring system follow-up will occur during the regularly scheduled monthly study visits. The follow-up will ensure that the monitors are placed on the refilled bottles of both medications and the MEMS caps are being used properly. During the visits, participants will complete a short four-item questionnaire that asks how the electronic monitors are being used. In addition, data collected from the monitors will be downloaded at each visit by the coordinator and sent electronically through a modem connection to a central database.

At completion of the study (i.e., weeks 24 or 48), the electronic monitoring system caps will be collected. Study sites will provide participants with \$25 for returning both caps undamaged.

Adherence Questionnaire. A detailed assessment of adherence is needed to understand whether variation in clinical outcomes is related to varying levels of adherence. This assessment is particularly important in individuals who fail maintenance therapy because failure may be related to behavioral variation subsequent to a change in therapy, characteristics of the new therapy, or low treatment efficacy. To distinguish between these potential factors, multiple measures of adherence and patient attitudes will also be assessed.

A self-reported adherence questionnaire will be administered at weeks 4, 12, 24, 36, and 48. The questionnaire will ask participants about any doses missed during each of the previous four days and how medications are being taken. In addition, nine "yes/no" questions regarding compliance with the medication schedule will be asked as well as reasons for missing doses.

Other measurement tools: Social support questionnaire, self-efficacy questionnaire (see Appendix 6) will also be administered at Screen 2 visit, and at Week 24, or at early termination visit for patients who discontinue prior to Week 24.

6.0 Data Analysis/Statistical Power

The study is designed to have 400 patients; 200 White/Caucasian, 200 Black/African American. There will be 80% power to detect a difference in the percentages of undetectable viral RNA 6 months following treatment (sustained virological response, SVR) between racial groups if the percentage of White/Caucasian patients with a SVR is 40% and the percentage in Black/African-American patients is 26% using a two-sided test with α = 0.05. In multivariable analyses, there will be 80% power to detect a difference if the percentages of SVR are 40% for Whites/Caucasians and 25% for Blacks/African Americans, assuming a multiple correlation coefficient of 0.4 between race and the other independent variables using a two-sided test with α = 0.05.

Primary analyses will be performed using all enrolled patients. Patients will be considered enrolled in the study upon taking the first dose of study medication. Participants who do not have outcome data will be included as treatment failures. We will also perform analyses that include only those participants with known outcome data.

Summary statistics will be generated to describe the study sample at baseline. Descriptive statistics, including measures of central tendency (e.g. means, medians) and estimates of spread (e.g., standard deviations) will be used for continuous variables such as age. Frequency distributions will be used for categorical variables such as education level. Ninety-five percent confidence intervals will be calculated for all point estimates of continuous data. Graphical displays (e.g. histograms, box plots) will also be used to describe the data. The baseline demographic information and viral characteristics of the racial groups will be compared using the chi-square test for association or exact tests for differences in proportions or trend in ordinal data. Continuous variables may be transformed, where appropriate, to meet the assumptions of parametric tests. The Student's t-test or a non-parametric alternative, the Wilcoxon rank-sum test, will be used to determine differences in the distribution of continuous data between the two racial groups.

The proportion of African Americans and Caucasians with SVR will be compared using the chi-square test of association. The association between race and SVR after adjusting for potential confounders such as adherence, HCV sub-genotype, initial viral level, ALT, body mass index, and baseline histology will be assessed through multiple logistic regression analyses. The Hosmer-Lemeshow statistic will be calculated to determine if there is evidence that the final multiple logistic regression model does not fit. ²³ These

analyses will be repeated for durable viral response, i.e., having undetectable viral RNA 12 months following treatment discontinuation.

Generalized estimating equation (GEE) methods of Zeger and Liang.^{24,25} will be used to assess the differences between the racial groups with respect to changes in serum HCV RNA levels during therapy. This approach models both the regression of the response variable on the independent variables and accounts for the correlated nature of the responses. Analyses using conventional regression methods could provide erroneous variance estimates and loss of statistical efficiency because of the conventional assumption that each response is statistically independent. As a result, invalid inferences could be made if the conventional approach were applied to these longitudinal data.

The models examining response to treatment will include measures of adherence. As an initial step in examining adherence, graphical displays of the dosing history of each participant will be plotted and compared to the prescribed dosing regimen. Graphs include chronological plots showing the date and time of dose intake and frequency histograms of inter-dose intervals. The inter-dose interval representing the length of time between two successive doses will be calculated. For ribavirin, the optimal inter-dose interval is 12 hours and for peginterferon it is 7 days. Longer dosing intervals represent non-adherence and times in which the participant theoretically did not have adequate inhibitory drug concentration. In addition, summary statistics of adherence such as the percentage of prescribed doses taken and the percentage of drug holidays will be derived from the MEMS cap data. GEEs with multiple responses and adherence as a time-dependent covariate will be examined.

We will also examine adherence as an outcome variable. Mutivariable analyses, using GEE methodology, will be employed to identify factors independently associated with adherence. The primary response variable examined in the analyses will be the dose intake per week for the 48 weeks of the study. Dose intake refers to the weekly doses of ribavirin and peginterferon consumed as recorded by the MEMS cap. Separate regression analyses will be performed to examine the effect of each medication.

We are also interested in examining the relationship between viral kinetics and outcome. Neumann et. al²⁶ and Zeuzem²⁷, discuss the two-phase decline in serum HCV RNA levels following the initiation of therapy consisting of the daily administration of interferon-2b. After an initial 8 to 10 hour pharmacokinetic period, there is an approximate 2.0 log (base 10) decline in serum HCV RNA levels during the next 48 hours by inhibiting viral production. From day 2 on, viral decline is markedly slower, which reflects the clearance of HCV infected liver cells. The viral kinetics following therapy with pegylated interferon and ribavirin may follow a different pattern, possibly reflecting a three-phase, rather than a two-phase, decline. The viral kinetics will be described using nonlinear regression methods to estimate parameters of models of viral infection for each patient. ²⁸ Then, the distributions of these parameters will be compared between racial groups using, for example, the Wilcoxon Rank Sum test. We will use generalized linear models to determine whether the parameters differ by race after adjusting for confounding factors that, ideally, would be specified in advance. Models may be fit for early phase (e.g., days 0-3) to see whether there are race differences in viral production, and for the later time period to see whether there are differences in virion clearance.

For all analyses, a p-value of less than 0.05 will be used to indicate statistical significance.

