2.0 Study Objectives and Endpoints

2.1 Specific Aims

1. To evaluate racial differences in response to antiviral therapy for chronic hepatitis C. Our hypothesis is that African Americans respond poorly to therapy for hepatitis C when compared to Caucasians with similar disease characteristics. Well-defined cohorts of African American and Caucasian patients with chronic hepatitis C (all genotype 1) will be treated with combination therapy (pegylated interferon and ribavirin) to determine differences in virological response rates between the two races.

2. Evaluate factors associated with resistance to antiviral therapy in African Americans and Caucasians with chronic hepatitis C. Pretreatment variables such as gender, history of alcohol use, HCV RNA levels, hepatic histology, among others, will be investigated to determine which factors may be associated with sustained virological response and how they may differ between racial groups. On-treatment variables will include viral kinetics, immunological responses, host response to interferon therapy, and adherence to therapy.

3. Evaluate differences in HCV viral kinetics in response to antiviral therapy and its relationship to sustained virological response. The rate of clearance from serum of HCV RNA will be compared between a cohort of African Americans and Caucasians to determine if racial differences exist, and between responders and non-responders to determine if they are predictive of treatment failure or success and if they are useful in the management of patients with chronic HCV.

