4.3 Baseline Visit (Day 0): Once the patient has completed the two screening visits and has been confirmed to be eligible, he/she will return for additional laboratory studies and comprehensive instruction in self-injection techniques by study personnel. These three visits, screening 1, screening 2, and baseline (day 0) will occur within 56 days.

Interim Medical History	
CBC/Differential	
Chemistry	ALT, AST, AlkPO4, total and direct bilirubin, fasting triglycerides, glucose, insulin
Serum Storage	Serum 3ml
Viral Genetics	
Patient Genetics	
Viral Kinetics	HCV RNA quantitative
Pharmacokinetics	Peginterferon alfa-2a levels, 2',5'-OAS serum activity
Interferon Signaling	
Pregnancy Test	Urine
Adherence MATI	
Medication Education	Self-injection techniques (including video), use of MEMS caps, adherence materials
Study Medication Administration	Supervised by research coordinator

Table 6 Baseline (Day 0) visit

4.4 Treatment Period: Pegylated interferon will be administered as a weekly subcutaneous injection and ribavirin will be administered as tablets twice daily. Treatment will be continued for 48 weeks (except in the absence of virological response as defined below). During the treatment period, participants will return for safety and efficacy evaluations at weeks 1, 2, 4, 6 (safety labs only), and 8, and then monthly until treatment is completed.

Efficacy assessment at week 24 will determine if participants are eligible to continue the full 48 weeks of treatment. Participants who have a positive qualitative test result, in duplicate, will be discontinued from study medication at week 24. These participants will then enter the follow-up period and be followed for an additional 24 weeks (post-treatment weeks 4, 12, 24). If they begin other antiviral therapy, they will be discontinued from follow-up.

Interim Medical History	
Symptom-directed Physical Exam	Vital signs and weight at each visit; physical exam every 3 months or as needed
Adverse Event Assessment	
Concurrent Medication Assessment	
CBC/Differential	Each visit (except days 1 and 2)
Chemistry	Each visit except week 1; ALT, AST, AlkPO4, total and direct bilirubin, albumin, uric acid, BUN, creatinine, glucose. Fasting triglycerides, glucose, and insulin at week 24, and week 48 for responders only.
Pregnancy Test	Urine, each visit (except days 1and 2)
TSH	Weeks 12, 24, 36, 48
PT/PTT	Weeks 24 and 48

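### The only adjusted race–SVR model specified includes adherence, an on-treatment variable, as a confounder, so its race odds ratio is not the Aim 1 difference at similar baseline disease characteristics

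*Protocol*

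**What the plan says.** Aim 1 (Protocol, Section 2.1) is the hypothesis that "African Americans respond poorly to therapy for hepatitis C when compared to Caucasians with similar disease characteristics".

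Section 6.0 gives two analyses of race and SVR:

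- **Unadjusted.** "The proportion of African Americans and Caucasians with SVR will be compared using the chi-square test of association".
- **Adjusted.** Multiple logistic regression "after adjusting for potential confounders such as adherence, HCV sub-genotype, initial viral level, ALT, body mass index, and baseline histology". Section 6.0 adds: "The models examining response to treatment will include measures of adherence". Both analyses are then repeated for durable response.

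Elsewhere the protocol treats adherence differently:

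- Aim 2 (Section 2.1): "On-treatment variables will include viral kinetics, immunological responses, host response to interferon therapy, and adherence to therapy".
- Section 5.0: "it remains unclear if adherence is a factor that explains the low SVR observed in African Americans as compared to Caucasians".
- Section 6.0, later: adherence is the outcome of its own generalized estimating equation model, with weekly dose intake over 48 weeks as the response.

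For scoring, Section 6.0 mentions "summary statistics of adherence such as the percentage of prescribed doses taken and the percentage of drug holidays", as examples. It does not say which measure enters the SVR model. Section 4.4 sets the stopping rule: "Participants who have a positive qualitative test result, in duplicate, will be discontinued from study medication at week 24".

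**The concern.** Race is not randomised, so the adjusted model is the one that addresses the similar-disease wording of Aim 1. Section 6.0 gives that model its own power statement, so it is meant for inference. A covariate that arises after treatment starts, and that may carry part of the racial difference, changes what the race coefficient means. It becomes the difference left after any part acting through adherence is removed, and it can also be distorted by causes shared by adherence and SVR. A reader of the results would take it for the difference at equal baseline disease. Part of a real gap could be reported as explained, or the gap could be overstated.

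**Working it through.** **1. The roles given to adherence.** A confounder must not itself be a result of the exposure. Race and disease characteristics precede treatment; adherence follows it. An on-treatment variable that may explain the gap, and that is modelled as an outcome, fits the description of a mediator. The other covariates named (sub-genotype, initial viral level, ALT, body mass index, histology) are, or can be taken as, baseline values. Adherence cannot.

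**2. The plan's own figure.** Section 6.0 states 80% power for the adjusted analysis: 200 per group, SVR 40% v 25%, multiple correlation 0.4 between race and the other covariates, two-sided α = 0.05.

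- Effective size per group: m = 200 × (1 − 0.4²) = 168; mean proportion 0.325.
- Power = Φ{[0.15 − 1/m − 1.96·√(2 × 0.325 × 0.675/m)] / √[(0.40 × 0.60 + 0.25 × 0.75)/m]}.
- At m = 168: (0.15 − 0.0060 − 0.1002)/0.0504 = 0.87, so 80.8% (83.8% without the 1/m continuity correction). The stated 80% reproduces.
- Dropping adherence cannot raise the multiple correlation. At the other limit, R = 0 and m = 200: (0.15 − 0.0050 − 0.0918)/0.0462 = 1.15, so 87.5%.

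A baseline-only model therefore keeps 80.8% to 87.5% power at 40% v 25%.

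**3. How far adjustment for adherence could move the odds ratio.** The unadjusted planning value, African American v Caucasian, is (0.26/0.74)/(0.40/0.60) = 0.527, with log −0.64. The protocol gives no adherence levels or effects, so these are assumptions: ten points more adherence adds 0.3 to the log odds of SVR, and mean adherence in Caucasians is 0.82. Then approximately

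adjusted log OR = −0.64 − 0.3 × (difference in mean adherence, African American minus Caucasian)/0.10.

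The simulation used 1,000,000 subjects with SVR held at 40% and 26%. Its last column assumes that 35% of patients without SVR are HCV RNA negative at week 24 in both groups.

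| Mean adherence, African American | Approximate OR | Simulated OR, share of prescribed doses | Simulated OR, share of a fixed 48-week course |
|---|---|---|---|
| 0.82 | exp(−0.64) = 0.53 | 0.52 | 0.50 |
| 0.76 | exp(−0.46) = 0.63 | 0.62 | 0.77 |
| 0.69 | exp(−0.25) = 0.78 | 0.75 | 1.22 |
| 0.87 | exp(−0.79) = 0.45 | 0.45 | 0.35 |

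In further runs with lower adherence in African Americans and an unmeasured common cause of adherence and SVR, a true direct odds ratio of 0.53 was estimated as 0.65 when that cause acted on both in the same direction. One of 0.60 was estimated as 0.52 when it acted in opposite directions. These runs used the share of prescribed doses.

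**4. The week-24 stop alone.** Assume that every patient with SVR is HCV RNA negative at week 24, and let q be the share of patients without SVR who are also negative then. Among those who continue, the odds of SVR are p/[(1 − p)q]. The odds ratio is therefore 0.527 × q(Caucasian)/q(African American):

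- 35% and 35%: 0.53
- 35% and 25%: 0.74
- 40% and 20%: 1.05
- 25% and 35%: 0.38

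This matters only if the adherence measure depends on course length.

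**The case against.** **The unadjusted test stands.** The chi-square comparison comes first, is powered separately (40% v 26%), has no adherence term and gives the total racial difference. A real gap would still be visible beside the adjusted result. This limits the severity.

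**Adherence belongs in the study.** Aim 2 lists it, and Section 5.0 asks whether it explains the gap. This also stands. The fault is the confounder label and the pooling with baseline covariates, not the study of adherence.

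**The covariate list is only illustrative.** A baseline-only model is not forbidden. But none is named, and the statement that response models will include adherence points the other way.

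**The named summaries are relative to prescription.** A patient stopped at week 24 has no doses prescribed afterwards, so the stop does not mechanically lower the share of prescribed doses taken. The 48-week dose-intake variable belongs to the separate model with adherence as outcome. This stands. Still, the summaries are examples, and a definition that Section 5.0 cites from earlier work includes the share of expected treatment duration, so a duration-dependent measure is not ruled out.

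**A stronger reading to avoid.** A reader might infer that the adjusted effect is biased toward the null, and that the stopping rule removes most of it. Section 1.1 gives a hint, since small studies suggest flat and nil responses are more common in African Americans. That concerns viral response, not adherence, and gives no week-24 rates for this regimen. With invented stop rates of 35% v 55%, and SVR only in those who continue, the odds ratio (Caucasian v African American) falls from 1.90 to (0.615/0.385)/(0.578/0.422) = 1.17, a loss of 76% of its log. At 40% v 50% it is (0.667/0.333)/(0.52/0.48) = 1.85, a loss of 4%. At 30% v 55% it is (0.571/0.429)/(0.578/0.422) = 0.97, a loss of 104%, that is, a reversal. The answer is whatever the assumption makes it.

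**Conclusion.** The point holds as a fault in specification. Followed as written, the adjusted race odds ratio is not the racial difference among patients with similar baseline disease characteristics, and the repeat for durable response inherits the problem. The mediator problem applies to any adherence measure. The mechanical link to virological response applies only to one tied to the 48-week course.

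Neither size nor direction can be stated. The protocol gives no racial difference in adherence, no effect of adherence in this regimen and no week-24 response rates. Under the assumptions above, an unadjusted 0.53 ranges from 0.45 to 0.75 with prescribed-dose adherence; these figures show sensitivity and are not forecasts. A claim of bias toward the null is not supported. Because the unadjusted test is unaffected, this is a cheap correction of moderate weight, not a threat to the trial's main comparison.

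**What to change.** - In Section 6.0, name a logistic regression of SVR on race plus baseline covariates only (sub-genotype, initial viral level, ALT, body mass index, histology) as the adjusted Aim 1 analysis. Do the same for durable SVR.
- Remove adherence from the list of confounders. Report the model that adds it separately, labelled as an explanatory (mediation) analysis under Aim 2, and note that common causes of adherence and SVR can distort it.
- Score adherence in that model as the share of prescribed doses taken within weeks 0–24, so that the week-24 stop does not enter the measure. State how doses after an earlier stop or a dose change are counted.
- Limit the sentence that puts adherence in all response models to the explanatory model.

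The cost is wording and one extra model, with no new data. The adherence-adjusted estimate becomes secondary.
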